5.2. PLANNED INTERIM ANALYSIS

None planned.

Document:

Author:

...\ITI\ITI-007\MYA11638\Biostatistics\Documentation\SAP\ITI-007-404 SAP Final V1.0 12JUN2019.docx

Version Number:1.0

[figure not shown]
Version Date: 12JUN2019

5.3. FINAL ANALYSIS

The final analyses detailed in this SAP will be performed by IQVIA Biostatistics following Intra-Cellular Therapies, Inc (ITCI) authorization of the SAP, ITCI authorization of Analysis Sets, final Database Lock and Unblinding of Treatment.

6. ANALYSIS SETS

6.1. ALL SUBJECTS ENROLLED [ENR] SET

The All Subjects Enrolled (ENR) Set will contain all subjects who signed the informed consent for this study.

6.2. ALL SUBJECTS RANDOMIZED [RND] SET

The All Subjects Randomized (RND) Set will contain all subjects who signed the informed consent and were randomized to study medication. Subjects will be classified according to randomized treatment for analyses and displays based on the RND Set.

6.3. INTENT-TO-TREAT [ITT] SET

The Intent-To-Treat (ITT) Set will contain all randomized subjects who received at least one dose of the study medication and who had a valid baseline (pre-dose) measurement and at least one valid post baseline measurement of MADRS total score. All analyses using the ITT Set will classify subjects according to the randomized treatment, regardless of the treatment received during the course of the study.

Document: Author:

...\ITI\ITI-007\MYA11638\Biostatistics\Documentation\SAP\ITI-007-404 SAP Final V1.0 12JUN2019.docx

Version Number:1.0

Version Date: 12JUN2019

6.6. SAFETY ANALYSIS [SAF] SET

The Safety Analysis (SAF) Set will contain all randomized subjects who received at least one dose of study medication. For all analyses using the SAF set, subjects will be classified according to treatment actually received. In case of incorrect dosing, the treatment most often received will be taken as the actual treatment.

7. GENERAL CONSIDERATIONS

Relative Study Day will be calculated from the date of Day 1, which is the day of first treatment with study medication (Study Day 1), and will be used to show the start and/or stop days of treatments, study procedures and assessments, prior, concomitant and post-treatment medications, and adverse events.

- If the date of the treatment, procedure, or event is on or after Study Day 1 date then: Relative Study Day = (date of variable of interest – Day 1 date) + 1.
- If the date of the treatment, procedure, or event is prior to the Day 1 date then:

Document: Author:

Page 14 of 53

Relative Study Day = (date of variable of interest – Day 1 date).

In the situation where the date is partial or missing, Relative Study Day, and any corresponding durations will appear missing in the listings.

Analyses presented by visit or study day will be based on the scheduled visits as planned in the protocol. Visit windows for unscheduled visits or early discontinuation visits are defined in Table A:, which provides the mapping of relative day ranges to the scheduled target days and the study periods. If more than one assessment is available in the same 'Range of Relative Study Days' (window), the assessment closest to the Scheduled Target Day will be selected and assigned to the Scheduled Target Day. If two or more assessments are available in the same window and are equidistant from the Scheduled Target Day, the latest assessment will be selected.

Listings will include scheduled, unscheduled, retest and early discontinuation data.

Table A: Mapping of Relative Day Ranges to Schedule Target Day

| Study Phase | Study Period | | Scheduled Target Day | Schedued Study |
|-----------------|---------------------|---|-------------------------|-------------------|
| | | Range of Relative Study Days | raigot bay | Week |
| Pre-Treatment | Screening | 1-14* days before Day 1 date | Day -14 | -2 |
| Pre-Treatment | Baseline | Day 1 date (definition of baseline varies by assessment – see descriptions below) | Day 1 | 0 |
| Study Treatment | On- Treatment | 2 to 11 days relative to Day 1 date | Day 8 | 1 |
| Study Treatment | | 12 to 18 days relative to Day 1 date | Day 15 | 2 |
| Study Treatment | | 19 to 25 days relative to Day 1 date | Day 22 | 3 |
| Study Treatment | | 26 to 32 days relative to Day 1 date | Day 29 | 4 |
| | | 33 to 39 days relative to Day 1 date | Day 36 | 5 |
| | | ≥40 days relative to Day 1 date and after the last dose of treatment and before the start of the Safety Follow-up Period (one day after actual Day 43 visit) | Day 43 | 6 |
| Post-treatment | Safety Follow-up | > 43 days relative to Study Day 1 date for treatment completers (42 days on-treatment) and after Day 43 post-treatment assessments. | Day 57 | 8 |

^{*} Not to exceed maximum allowed days

Baseline assessments are scheduled for Visit 2 on Relative Study Day 1, prior to first treatment of study medication. Unless otherwise specified, baseline is defined as the last non-missing measurement before the first dose of study medication.

Assessments will be considered baseline if the date of the last pre-treatment measurement is before the date of the first treatment or if the measurement was done on Study Day 1 and, according to the Study Schedule of Events, was supposed to be performed on Day 1, prior to treatment (including unscheduled measurements).

For parameters planned to be collected multiple times at the same time point (3-positional

Document: ...\ITI\ITI-007\MYA11638\Biostatistics\Documentation\SAP\ITI-007-404 SAP Final V1.0 12JUN2019.docx Author: Version Number:1.0

Version Date: 12

Page 15 of 53

blood pressure), the average of the last non-missing pre-treatment measurements will be considered as baseline.

Unless otherwise specified, the following calculations will be used for change from baseline and percent change from baseline:

Change from baseline visit will be calculated as:

Value at Visit X – Baseline Value

Percent change from baseline will be calculated as:

• Value at Visit X – Baseline Value

Baseline Value × 100

All investigative sites with fewer than 4 ITT subjects will be pooled as follows: The largest site with fewer than 4 ITT subjects will be pooled with the smallest site with fewer than 4 ITT subjects. If this results in a pooled site still having fewer than 4 ITT subjects, this site will be pooled together with the next smallest investigative site, if one exists; otherwise, no further pooling is needed. Sites with the same number of ITT subjects will be ordered in ascending order of their numerical site identification number. This will serve as a tie-breaker rule in case multiple sites have the same number of ITT subjects. If the primary efficacy analysis model, described in section 15.1.3 presents convergence issues due to the too small number of subjects per site, the same site pooling algorithm will be applied again, but this time pooling sites with fewer than 8 ITT subjects. Should the primary efficacy analysis model still present convergence issues, after testing the sequence of correlation structures listed in section 15.1.3, then including the site effect in the model will be reconsidered and may be dropped. These pooled investigative sites, as determined based on the primary efficacy response variable, will be used for any analysis that has investigative site as a fixed effect in the model. The actual investigative site numbers will be included in the by-subject listings.

The default significance level for statistical tests will be 5%; confidence intervals (CIs) will be 95% and all tests will be two-sided, unless otherwise specified in the description of the analyses. All analyses will be conducted using SAS® version 9.4 or higher.

7.1. MISSING DATA

The total and subscale scores of any assessment with more than one item, such as MADRS, CGI-BP-S, YMARS, CSSR-S, Q-LES-Q-SF, AIMS, BARS and SAS, will be derived from the individual items. Any individual missing item in any scale will not be imputed. If one or more items are missing at a visit, then the associated total score or subscale score will be set to missing.

The main objective of the analyses in this study is to evaluate treatment effect of 60 mg ITI-007 compared to placebo if the treatment is administered for the planned treatment duration. In order to evaluate this estimand in the presence of subjects that may discontinue treatment prematurely, the primary efficacy analysis will be performed based on the assumption of data being missing at random (MAR). This implies that subjects discontinuing from treatment early are considered to have unobserved values similar to the observed ones

Document: ...\ITI\ITI-007\MYA11638\Biostatistics\Documentation\SAP\ITI-007-404 SAP Final V1.0 12JUN2019.docx
Author: Version Number:1.0

Page 16 of 53

in their respective treatment group for subjects who have similar history, i.e., the distribution of the unobserved future values for subjects who had discontinued treatment is the same as the distribution of the observed values for those subjects who completed treatment, conditional on the available data prior to discontinuation.

The Mixed-Effects Model for Repeated Measures (MMRM) method will be used for the analysis of the primary and key secondary efficacy endpoints. The MMRM approach does not impute missing data but is based on all subjects included in the analysis set using all available longitudinal data (either complete or partial). This approach is based on the MAR assumption as described above.

Document: Author:

 $... \label{lem:likelihoof} \verb|MYA11638| Biostatistics| Documentation| SAP | Final V1.0 12 | JUN2019. docx | Continuous |$

Version Number: 1.0

STATISTICAL ANALYSIS PLAN: PROTOCOL ITI-007-404
Page 17 of 53

8. OUTPUT PRESENTATIONS

The Tables, Listings and Figures (TLFs) shells provided with this SAP describe the presentations for this study and therefore the format and content of the summary TLFs to be provided by IQVIA Biostatistics.

Continuous variables will be summarized using descriptive statistics (number of subjects [n], mean, standard deviation [SD], median, minimum, and maximum, unless otherwise stated). The minimum and maximum will be reported to the same number of decimal places as the raw data recorded in the database. The mean and median will be reported to one more decimal place than the raw data recorded in the database. The SD will be reported to two more decimal places than the raw data recorded in the database.

Categorical variables will be summarized using frequency counts and percentages. Unless otherwise stated, the calculation of percentage will be based on the number of subjects in the analysis set of interest.

P-values will be presented to three decimal places. P-values less than 0.001 will be presented as "<0.001".

Confidence intervals (CIs) will be presented to two more decimal places than the raw data.

Source data for summary tables and statistical analyses will be presented as subject data listings.

9. DISPOSITION AND WITHDRAWALS

Subject disposition and withdrawals will be presented by treatment group, when applicable, and overall for the ENR Set.

The number and percentage of subjects who were screened, screen failed, randomized, completed or discontinued the 6-week On-Treatment Period and completed or discontinued the study, and reasons for treatment discontinuation and study discontinuation will be presented. The reasons for study withdrawal and treatment discontinuation are listed in Table B:.

The reasons for treatment discontinuation will also be presented by treatment group and by time to treatment discontinuation, categorized based on the planned visits (≤ Day 8, > Day 8 -

Document: ...\ITI\ITI-007\MYA11638\Biostatistics\Documentation\SAP\ITI-007-404 SAP Final V1.0 12JUN2019.docx Author: Version Number:1.0

Page 18 of 53

 \leq Day 15, > Day 15 - \leq Day 22, > Day 22 - \leq Day 29, > Day 29 - \leq Day 36, > Day 36 - \leq Day 43) for all subjects in the SAF Set. The reasons for study discontinuation and treatment discontinuation are listed in Table B.

A subject is defined to have completed treatment if the subject completed the 6-week On-Treatment period as recorded on the End of Treatment CRF page.

A subject is defined to have completed the study if the subject has completed the 6-week On-Treatment Period and the end of study follow-up assessments as recorded on the End of Study CRF page.

Reasons for Study Withdrawal and Study Medication Discontinuation Table B: **Terminology**

| Case Report Form Terminology | Study | Study Medication |
|---|-------|---------------------|
| Screen failure | Х | |
| Adverse event | X | Х |
| Adverse event associated with worsening of bipolar depression* | X | X |
| Adverse event not associated with worsening of bipolar depression* | X | X |
| Death | Х | Х |
| Lack of efficacy | Х | X |
| Lost to Follow-up | Х | |
| Protocol violation | Х | X |
| Physician decision | Х | X |
| Study terminated by sponsor | Х | X |
| Subject withdrew consent: | Х | X |
| Personal or family reasons; | X | X |
| Refused to provide a reason or refused all end-of-study procedures; | X | X |
| Self-reported adverse event; | X | X |
| Self-reported lack of efficacy | X | X |
| Other | Х | Х |

^{*} Adverse event associated with worsening of bipolar depression will be identified by a Medical Monitor review prior to database lock.

The number and percentage of randomized subjects who discontinued due to an adverse event associated with worsening of bipolar depression will be summarized. The number and percentage of randomized subjects discontinued due to an adverse event not associated with worsening of bipolar depression will also be presented.

...\ITI\ITI-007\MYA11638\Biostatistics\Documentation\SAP\ITI-007-404 SAP Final V1.0 12JUN2019.docx Document: Author:

Version Number:1.0

INTRA-CELLULAR THERAPIES INC. (ITCI)

STATISTICAL ANALYSIS PLAN: PROTOCOL ITI-007-404

Page 19 of 53

The time to treatment discontinuation due to all reasons, adverse events, lack of efficacy, or due to any other reason of special interest will be evaluated separately using the Kaplan-Meier method. Time to treatment discontinuation of subjects in the SAF Set will be defined as the date of discontinuation minus date of first dose of study medication plus 1. Subjects who complete treatment or who discontinue for a reason other than the one being evaluated will be censored. The Log-rank test will be used to compare the time to treatment discontinuation between the 60 mg ITI-007 treatment group and placebo group. The same analysis will be repeated for time to treatment discontinuation for any reason, where only subjects who complete the 6-week Treatment Period will be censored.

The number and percentage of subjects who withdrew from the study will be summarized by visit, treatment group and overall for all subjects in the RND Set. The number of subjects randomized will also be summarized by site for the RND Set. The number of subjects remaining on treatment over time will be presented in a figure.

| The number and percentage of subjects in the RND set. | f subjects in the SAF set, the ITT set will be summarized by treatment group and overall for all |
|---|--|
| | |
| | |
| | |
| | |
| | |
| | |
| | |

Document: Author: ...\ITI\ITI-007\MYA11638\Biostatistics\Documentation\SAP\ITI-007-404 SAP Final V1.0 12JUN2019.docx Version Number:1.0

11. Demographic and other Baseline Characteristics

Demographic data and other baseline characteristics will be presented for the ITT and SAF Sets.

No formal statistical testing will be carried out for comparing demographic or other baseline characteristics between the two treatment groups.

The following demographic and other baseline characteristics will be reported:

Demographics

- o Gender
- Age (years) calculated as (Date of Informed Consent Date of Birth)/365.25
- Age category (<=40 years and >40 years)
- Race
- Ethnicity

Other Baseline Characteristics

- o Height (cm)
- Weight (kg)
- Waist circumference (cm)
- Body Mass Index (BMI) (kg/m²) calculated as weight (kg) / height (m)²

Consumption Habits

- Alcohol
- o Caffeine
- o Tobacco
- Cannabis

Document: Author: $...\ \ ITI\ ITI-007\ MYA11638\ Biostatistics\ Documentation\ SAP\ ITI-007-404\ SAP\ Final\ V1.0\ 12JUN2019. docx$

Version Number:1.0

Page 21 of 53

Bipolar Disorder Diagnosis

- Bipolar disorder diagnosis (Bipolar I or II);
- Age at first diagnosis of Bipolar Disorder (years);
- Duration of current major depressive episode (weeks);
- Number of lifetime depressive episodes;
- Hospitalization for emotional or psychiatric problems;
- Number of hospitalizations in lifetime:
- Hospitalization in the past year;

Baseline Efficacy

Baseline efficacy parameters, including MADRS total score, MADRS item 4 score, CGI-BP-S subscale scores, CGI-BP-S total score and Q-LES-Q-SF score

Bipolar Disorder Baseline Safety

 Baseline safety parameters, including total scores for the following: SAS, AIMS, BARS, YMRS, and CSSR-S

12. **MEDICAL HISTORY**

Medical history information will be presented for the SAF Set and will be coded using a current version of the Medical Dictionary for Regulatory Activities (MedDRA).

Medical History conditions are defined as those current and past conditions at Screening.

The number and percentage of subjects with at least one pre-existing condition as well as the number of subjects having pre-existing conditions will be summarized by system organ class (SOC), preferred term (PT), treatment group and overall. For each subject, multiple reports of pre-existing conditions that map to a common PT and SOC will be condensed into a single medical history for incidence counts.

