12.4.1 Patient Disposition, Analysis of Demographics and Other Baseline Characteristics

Patient disposition will be summarized by treatment group, when applicable, and overall, including incidence of screening failure and incidence of treatment or study discontinuation and the corresponding reasons. The number and percentage of randomized patients who discontinued due to an AE associated with worsening of

bipolar depression will be summarized. Similarly, the number and percentage of randomized patients who discontinued due to an AE not associated with worsening of bipolar depression will also be presented. Time to discontinuation due to all reasons, AEs (all, AEs associated with worsening of bipolar depression, and AEs not associated with bipolar depression), lack of efficacy, or due to any reason of special interest will be evaluated using the Kaplan-Meier method, where patients who complete the On-treatment Period or who discontinue for a reason other than the one being evaluated, will be censored. The Log-rank test will be used to compare the time to discontinuation between the treatment groups.

Demographic and baseline characteristics, including Bipolar Disorder diagnosis and baseline efficacy parameters, will be listed and summarized by treatment group. No inferential statistics will be presented.

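### Kaplan-Meier by reason for stopping, with other reasons censored, does not estimate the probability of stopping for that reason; the excess is small and affects disposition only

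*SAP*

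**What the plan says.** SAP section 9 (Disposition and Withdrawals) states that time to treatment discontinuation for all reasons, adverse events, lack of efficacy or another reason of special interest "will be evaluated separately using the Kaplan-Meier method". The censoring rule follows: patients who complete treatment and those "who discontinue for a reason other than the one being evaluated will be censored". The arms are then compared: "The Log-rank test will be used to compare the time to treatment discontinuation between the 60 mg ITI-007 treatment group and placebo group". The analysis is repeated for discontinuation for any reason, "where only subjects who complete the 6-week Treatment Period will be censored".

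Protocol 12.4.1 has the same rule: time to discontinuation "will be evaluated using the Kaplan-Meier method", and "patients who complete the On-treatment Period or who discontinue for a reason other than the one being evaluated, will be censored". It also divides adverse-event discontinuations into those associated and those not associated with worsening of bipolar depression.

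SAP section 9 plans crude summaries too: "reasons for treatment discontinuation and study discontinuation will be presented". For treatment discontinuation, the reasons are also tabulated by arm and by visit interval up to Day 43 on the Safety Analysis (SAF) Set, the set used for the time-to-discontinuation definition. Neither document, in the text available, mentions cumulative incidence or competing events.

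**The concern.** Kaplan-Meier censoring removes a patient from the risk set on the assumption that he or she would later have had the event at the same rate as those who remain. For a patient who stopped for lack of efficacy, a later stop for an adverse event cannot happen. One minus the Kaplan-Meier estimate therefore describes a setting in which no other reason for stopping exists. It is not the proportion of patients who stop for that reason in this trial.

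Two things are at stake, both descriptive. The reason-specific estimates would disagree with the crude percentages planned for the same patients, and together they can add up to more than the any-reason estimate. The excess also depends on how often patients in an arm stop for other reasons, so two arms with the same proportion stopping for adverse events can show different estimates.

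**Working it through.** **Inputs from the documents.** A fixed 6-week treatment period (SAP 4.1). About 350 patients randomised 1:1 (protocol 12.1), so 350 / 2 = 175 per arm, taking all as dosed. The only discontinuation rate stated is 10% before the first post-dose MADRS (protocol 12.1). There is no six-week rate and no rate by reason, so there is no figure of the plan's own to reproduce.

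**Assumptions.** The six-week rates by reason below are assumed. Each patient either stops for one reason or completes treatment.

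**Formula.** Let a be the true proportion stopping for the reason of interest, b the proportion stopping for other reasons, and D = a + b. With the two cause-specific hazards in constant ratio over the period:

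- total cumulative hazard: H = −ln(1 − D)
- true cumulative incidence at six weeks: a
- one minus Kaplan-Meier (1−KM), others censored: 1 − exp(−H × a/D)

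| a (AE) | b (other) | H | H × a/D | 1−KM | Excess (points) |
|---|---|---|---|---|---|
| 6% | 9% | 0.1625 | 0.0650 | 6.29% | 0.29 |
| 8% | 17% | 0.2877 | 0.0921 | 8.79% | 0.79 |
| 5% | 25% | 0.3567 | 0.0594 | 5.77% | 0.77 |

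The relative excess is about 5%, 10% and 15%. Out of 175 patients, 0.29 to 0.79 points is 0.5 to 1.4 patients.

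**Wider range.** For D from 5% to 40%, with 10% to 75% of stops due to the reason of interest, the excess runs from 0.01 to 2.54 points (0.6% to 24.5% relative). At D of 20% or less it is at most 0.56 points.

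**Additivity.** In the 8% and 17% case, the estimate for other reasons is 1 − exp(−0.2877 × 17/25) = 17.8%. The two estimates sum to 8.8% + 17.8% = 26.6%, against 25% for any reason.

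**Timing.** Take 175 patients, 10 stops of interest and 25 competing stops. The crude percentage and the cumulative incidence are both 10/175 = 5.71%.

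- Competing stops all later: 1−KM = 10/175 = 5.71%, no excess.
- Stops spread evenly: 6.17%.
- Competing stops all first: 150 remain at risk, and 1−KM = 10/150 = 6.67%.

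With 42 competing stops the last two become 6.55% and 10/133 = 7.52%.

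**Arm comparison.** Take 6% stopping for adverse events in both arms.

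- 5% stopping for other reasons: H = −ln(0.89) = 0.1165, and 1 − exp(−0.1165 × 6/11) = 6.16%.
- 25% stopping for other reasons: H = −ln(0.69) = 0.3711, and 1 − exp(−0.3711 × 6/31) = 6.93%.

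The spurious gap is 0.77 points, despite a 20-point imbalance in other stops. The effect need not enlarge a difference: 8% adverse event with 9% other gives 8.40%, and 5% with 17% gives 5.49%, so a true difference of 3.0 points appears as 2.9.

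**The case against.** The strongest reply is that correct figures are already planned. With a fixed six-week period, cumulating the SAF Set table of reasons by visit interval gives the cumulative incidence at visit resolution. SAP 16.1.1 also reports adverse events leading to withdrawal or to stopping study medication as frequencies and percentages, so the headline rate of stopping for adverse events will be a crude percentage. The between-arm test is the log-rank, which remains valid for cause-specific hazards. All of this stands, and it keeps the point minor.

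Three stronger readings are tempting, and the documents do not support them.

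- A reader might infer that the SAP will show tolerability curves next to an any-reason curve that they visibly contradict. SAP section 9 names Kaplan-Meier evaluations, and the only figure it specifies there is the number of patients remaining on treatment. Format and content are left to the table and figure shells (SAP section 8), which are not available here. The overstatement arises only if one minus the Kaplan-Meier estimate is reported or read as a probability of stopping for that reason.
- A reader might infer that the estimate is always too high. It equals the true proportion when the competing stops come after the stops of interest.
- A reader might infer that a meaningful part of any arm difference in adverse-event stopping would be an artefact of lack-of-efficacy dropout. No rates by reason are given, the calculated gap is under 1 point even with very unequal competing stops, and the effect can shrink a difference as well as create one.

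What the objection does not remove is that both documents prescribe an estimator that, on its natural reading, answers a different question from the crude tables for the same patients.

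**Conclusion.** The concern holds as a minor point about the reason-specific estimates. Read as a probability, one minus Kaplan-Meier with other reasons censored is at or above the true proportion stopping for that reason, and above it whenever competing stops precede stops of interest. Under the assumed rates (5% to 8% adverse event, 9% to 25% other, constant ratio of hazards) the excess is about 0.3 to 0.8 percentage points. It would exceed 1 point only with total discontinuation of around 30% to 40%, and the documents do not indicate what rate to expect. A spurious arm gap stays under 1 point at 5% versus 25% other stopping.

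The any-reason Kaplan-Meier analysis, the log-rank comparison of cause-specific hazards, the crude percentages by reason, and the primary and key secondary results are not affected.

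**What to change.** In SAP section 9:

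- Keep Kaplan-Meier for discontinuation for any reason.
- For adverse events, lack of efficacy and each other specific reason, replace one minus Kaplan-Meier with the Aalen-Johansen cumulative incidence, treating all other reasons for stopping as competing events. The six-week values will then agree with the crude percentages on the SAF Set and add up to the any-reason figure.
- Keep the log-rank test for each reason, labelled as a comparison of cause-specific hazards.

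No new data are needed, and the estimator is standard. Because protocol 12.4.1 prescribes the present method, this is a departure. Protocol section 12 lets the SAP document such a change without a protocol amendment and requires it to be justified in the study report. That small, documented departure from the protocol text is the only cost.
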